2 STUDY OBJECTIVES

Primary Objective (PO):

To characterize the safety of authorized and recommended COVID-19 vaccines among children and adolescent participants

Secondary Objective (SO):

To assess the safety of simultaneous administration of COVID-19 vaccine with other routinely recommended vaccines among children and adolescent participants

Exploratory Objectives (EO):

EO 1: To assess adolescent and parent perceptions of the COVID-19 vaccine recommendations and experience with receipt of the vaccine

EO 2: To assess the safety of COVID-19 vaccine stratified by baseline COVID-19 serostatus (positive versus negative) in a subset of child and adolescent participants

EO 3: To assess adverse events of special interest through 6 months after dose 2 of COVID-19 vaccine or a booster dose

EO 4: To assess serious adverse events through 6 months after dose 2 of COVID-19 vaccine or a booster dose

EO 5: To assess immune responses to SARS-CoV-2 antigens after COVID-19 vaccine

Primary Outcome Measures (POM):

POM 1: Proportion of participants with defined local or systemic reactogenicity events (stratified according to severity and in total) on days 1-7 after each dose of COVID-19 vaccine

POM 2: Proportion of participants with at least one severe (Grade 3) solicited local or systemic reactogenicity event on days 1-7 after each dose of COVID-19 vaccine

POM 3: Proportion of participants with at least one moderate-to-severe (Grade 2-3) solicited local or systemic reactogenicity event on days 1-7 after each dose of COVID-19 vaccine

POM 4: Proportion of participants with an unsolicited adverse event on days 1-7 after each dose of COVID-19 vaccine

POM 5: Proportion of participants with an adverse event of special interest through 29 days after dose 2 of COVID-19 vaccine or a booster dose

POM 6: Proportion of participants with at least one serious adverse event occurring through 29 days after dose 2 of COVID-19 vaccine or a booster dose and a description of the serious adverse events

Secondary Outcome Measure (SOM):

SOM: Assessment of primary outcome measures 1-6 in those receiving other routinely recommended vaccines simultaneously with each dose COVID-19 vaccine versus those receiving COVID-19 vaccine alone

Exploratory Outcome Measures (EOM):

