5 STUDY SCHEDULE, PROCEDURES, & EVALUATIONS

5.1 Schedule of Events

Children and adolescents meeting the proposed eligibility criteria (**Section 4.0**) will be recruited. Written informed consent will be obtained from study participants or their parent/guardian and assent from participants per local IRB requirements prior to conducting any study procedures. **Table 1** describes the schedule of study visits for children enrolling with their first COVID dose.

Table 1: Schedule of events: Primary Series (Dose 1 and 2)		Visit 1	Visit 1a	Visit 2	Visit 2a	Visit 3	Visit 4
Procedure	Type of contact	Clinic	Phone/Text /Email/Data Review a, b	Phone/Data Review c	Phone/Text/Email/Data Review a, b	Clinic/Phone d	Phone/Data Review
Time Relative to 1st COVID-19 Vaccine	1 (-3)	1-7 (+3)					
Time Relative to 2nd COVID-19 Vaccine			1 (+3)	1-7 (+3)	29 (+ 7)	181 (+/- 7)	
Informed consent & Medical Release of Information	X						
Review Eligibility Criteria	X						
Data Collection (Demographic information and Medical History)	X						
COVID-19 Vaccination History	X						
COVID-19 Disease History	X	X	X	X	X	X	
Concomitant Medications and Vaccines	X	X	X	X	X	X	
Standard of Care COVID-19 Vaccine	X		X				
Memory aid training + supplies (training on temperature)	X		X				
Blood draw ^e	X ^f				X		
Staff to review Memory aid form (REDCap or paper)		X	X	X			
Obtain solicited adverse events		X	X	X			
Obtain unsolicited adverse events		X	X	X			
Obtain serious adverse event information and AESIs		X	X	X	X	X	
Obtain parental and adolescent perceptions of COVID vaccine recommendations and receipt ^g		X		X			
Confirm date of next vaccine	X	X					
Confirm next study visit	X	X	X	X	X	X	

a. Memory aid (solicited local and systemic reactogenicity events) to be completed by LAR/participant on Days 1-7 after vaccination.

b. LAR/Participants completing paper diary only will be called 3 [+3] days after each dose of vaccine as a reminder and to prompt to bring paper diary to next visit

c. May be clinic visit if COVID vaccine is administered at research site

d. May be phone visit if not obtaining immunogenicity labs

e. Blood draws are optional and will be only performed at participating sites

f. Blood draw may be performed 3 days before or after vaccine

g. Adolescent perceptions of COVID-19 vaccine will be collected for adolescents (ages 12 - < 16 only)

Visit 1, Day of Vaccine or up to 3 Days Prior - Screening, Enrollment, and Vaccination (Clinic Visit)

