Visit 2, COVID-19 Vaccine Dose 2 (+ 3 Days) (Clinic or Phone Visit)

- Confirm receipt of second dose of COVID vaccine
- Record any AEs, AESIs, SAEs, and concomitant medications and vaccinations as described in **Section 5.5**.
- Record clinical data related to COVID-19 diagnoses
- Confirm preferred method of contact for follow-up (telephone, email, or text reminder)
- Review instructions for use of thermometer, ruler, and memory aid completion.

Visit 2a, Days 1 - 7 Days after dose 2 (Phone Visit)

- Subjects/parent/LAR will complete their memory aid via paper or electronic entry at approximately the same time each day for days 1-7, study staff will review subject-entered data within the database or by phone contact
- For participants using REDCap web-based system:
 - Study staff will send daily reminders to fill out the symptom diary
 - Record clinical data related to COVID diagnoses
 - Study staff will review REDCap system to confirm data capture and assess for any AE, AESIs, or SAEs on day 3 and 7 after vaccine

- If any missing values, reported hives, or Grade 3 or greater events occurred, the study staff will use phone contact to gather more information
- The second parental and adolescent (if applicable) survey will be administered on day 7 after vaccine
- For participants using paper diary:
 - Study staff will call participants on day 3 after vaccine as a reminder to fill out the symptom diary
 - The second parental and adolescent (if applicable) survey will be administered on day 7 after vaccine
 - Study staff will call participants on day 7 (+ 3 days) after vaccine
 - Record symptom diary
 - Record COVID-19 diagnoses
 - Record second parental and adolescent (if applicable) survey

Visit 3, 28 Days (window days 29-35) after COVID-19 Dose 2 (Clinic Visit or Phone Visit)

- Clinic visit for optional post-vaccination blood draw for immunogenicity studies
- If no blood draw, may be a phone visit
- Review concomitant medications and vaccinations.
- Solicit for the occurrence of any adverse events of special interest or serious adverse events.

Visit 4, 180 days (window Days 174 - 188) after Dose 2 (Phone Visit)

- Record any SAEs or adverse events of special interest as described in **Section 5.5**
- Obtain concomitant medication and vaccine use

Table 2 describes the schedule of study visits for children enrolling with their COVID-19 booster dose.

Table 2: Schedule of events: Booster Dose

Procedure	Visit 1	Visit 1a	Visit 2	Visit 3

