5.5 Reactogenicity & Safety Assessment

Frequency and occurrence of local and systemic reactogenicity events will be assessed through post-vaccination Day 7 using a standard memory aid. At the time of study enrollment, participants will be given a thermometer and instructed on using the memory aid to document oral temperatures and post-injection symptoms. Beginning on the evening following the first COVID-19 vaccination, LARs/participants will record the participants oral temperature using the study-supplied thermometer, the occurrence of solicited and unsolicited AEs, and concomitant medication use for the next 7 days (Day 1 – 7). Similarly, following the second COVID-19 vaccination, LARs/participants will record the participant's oral temperature using the study-supplied thermometer, the occurrence of solicited and unsolicited AEs, and concomitant medication use for the next 7 days. Temperature will be recorded at roughly the same time each day. If a temperature $> 100^{\circ}\text{F}$ (37.8°C) is recorded, a second measurement will be taken. If more than one temperature is taken on the same day, the highest temperature should be recorded. Fever will be defined as a measured temperature $\geq 100.4^{\circ}\text{F}$ (38°C). Participants will be queried during Visits 1a and 2a on solicited injection site adverse events, which will be classified as mild, moderate, or severe as described in **Table 4**. Participants will also be queried during Visits 1a and 2a on common post-injection systemic symptoms as described in **Table 5**.

Unsolicited adverse events (AEs) will be collected and reported for the 7 days following each vaccine. Any reports of new rash within 7 days after each dose will prompt a call from the study team to ascertain severity and the likelihood of an allergic reaction. Concomitant medication use, and concomitant vaccinations will be assessed through 29 days after dose 2 or a booster dose. Serious adverse events (SAEs), adverse events of special interest (AESIs) and unscheduled medical care for COVID-19 illness will be assessed at 29 days after dose 2 of COVID-19 vaccine or a booster dose and through the end of the study (181 days after dose 2).

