Study site investigators will assess relatedness to COVID-19 vaccine or study procedures (related, possibly related, unlikely related, or not related) for SAEs and AESIs. Solicited symptoms in **Tables 4 and 5** will all be considered to be related to COVID-19 vaccine and causality assessment will not be done for these events. The study investigators will use their clinical judgement to make causality assessments and may consult the Safety Review Panel or CISA Project for assistance with causality determinations. The final causality assessment decision is the responsibility of the site PI where the subject was enrolled.

Reporting Adverse Events

SAEs and unanticipated problems will be reported to the CDC and all participating IRBs according to institutional requirements. Vaccination is not a study procedure.

Adverse events that occur in a recipient following COVID-19 vaccination should be reported to CDC's Vaccine Adverse Event Reporting System (VAERS). Vaccination providers are required by the Food and Drug Administration to report the following that occur after COVID-19 vaccination under Emergency Use Authorization:

- Vaccine administration errors
- Serious adverse events
- Cases of Multisystem Inflammatory Syndrome
- Cases of COVID-19 that result in hospitalization or death

Reporting is encouraged for any other clinically significant adverse event even if it is uncertain whether the vaccine caused the event. Information on how to submit a report to VAERS is available at <https://vaers.hhs.gov> or by calling [name].

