7.2.2 Primary Objective

Primary Objective – To characterize the safety of authorized and recommended COVID-19 vaccines among children and adolescent participants

1) Tables will be produced that summarize each solicited local and systemic reactogenicity event by maximum classification (none, mild, moderate, and severe), as well as by moderate or severe through days 1-7 following COVID-19 vaccination for dose 1 and dose 2 or a booster dose. These tables will have the number and percentage for each classification and will be broken down by each site and across all sites. In addition, the number and percentage of participants with at least one moderate-to-severe local or systemic reactogenicity event will be described, as well as the proportion of participants with at least one severe local or systemic reactogenicity event. (POM 1, POM 2 and POM 3)

2) Tables will be produced that summarize each unsolicited adverse event by maximum classification (none, mild, moderate, and severe), as well as by moderate or severe through days 1-7 following COVID-19 vaccination for dose 1 and dose 2 or a booster dose. These tables will have the number and percentage for each classification and will be broken down by each site and across all sites (POM4).

3) Tables will be produced that summarize participants experiencing at least one serious adverse event or one AESI through the 29 days after dose 2 or a booster dose. This table will have the number and percentage for each outcome. Listings with the clinical narratives will also be provided. (POM5 and POM6)

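### No pre-dose record of the systemic symptoms is scheduled, yet every solicited symptom on Days 1-7 is deemed vaccine-related; read as reactions, POM 1-3 are biased upward by an unknown amount

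*Combined protocol and SAP*

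**What the plan says.** **Start of recording.** For dose 1, Section 5.5 states: "Beginning on the evening following the first COVID-19 vaccination, LARs/participants will record the participants oral temperature using the study-supplied thermometer". For dose 2: "Similarly, following the second COVID-19 vaccination, LARs/participants will record the participant's oral temperature". Both begin after the injection.

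**Schedule.** In Section 5.1, the row "Obtain solicited adverse events" is blank at Visit 1 in Table 1 (primary series) and Table 2 (booster). The only temperature item at Visit 1 is "Memory aid training + supplies (training on temperature", which is instruction, not a reading. The Visit 1 lists cover medical, vaccine and COVID-19 history and concomitant medications, but not current symptoms. Table 3 describes medical history as significant conditions. Table 1 does mark solicited events at Visit 2, but that contact falls on Day 1 (+3) relative to dose 2, may be by phone, and its first task is "Confirm receipt of second dose of COVID vaccine".

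**Outcome and analysis.** POM 1 (Section 2) is "Proportion of participants with defined local or systemic reactogenicity events (stratified according to severity and in total) on days 1-7 after each dose". Section 7.2.2 reads: "Tables will be produced that summarize each solicited local and systemic reactogenicity event by maximum classification (none, mild, moderate, and severe". Neither requires the event to be new or worse than before the dose.

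**Attribution.** Under Causality (relatedness) Assessment in Section 5.5, the Table 4 and Table 5 symptoms "will all be considered to be related to COVID-19 vaccine and causality assessment will not be done for these events".

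**Comparator.** Section 5.3.1 says there is no randomization, and Section 7.2.1 defines one cohort, all vaccinated.

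**The concern.** Most Table 5 items (headache, fatigue, nausea, diarrhea, muscle pain and so on) are non-specific. A child who has one of them at the time of the dose and still has it at the first diary entry is counted in POM 1 and, depending on grade, in POM 2 or POM 3. The plan then labels the symptom as related without review.

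A study with an unvaccinated arm could subtract such background. This one cannot, so a pre-dose record is the only planned-data route to separating a symptom that was already there from one that began afterwards. If it is not collected, no later analysis can recover it.

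POM 1-3 belong to the primary safety result, so what is at stake is whether the reported proportions can be presented as reactions to the vaccine or only as symptoms in the week after it.

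**Working it through.** **1. Is there any pre-dose check?** Set side by side:

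| Dose | Contact nearest the dose | Solicited-event row | Pre-dose symptoms or temperature? |
|---|---|---|---|
| Dose 1 | Visit 1, Day 1 (-3) | blank | none listed |
| Dose 2 | Visit 2, Day 1 (+3) | marked | no; the contact confirms a dose already received |
| Booster | Visit 1, Day 1 (-3) | blank | none listed |

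The nearest filter is exclusion 2 in Section 4.2, a general investigator-opinion criterion. It names neither acute illness nor fever. Under Section 4 it is reviewed at Visit 1, which may precede the dose by 3 days, and it does not apply again at dose 2.

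**2. Is there a figure to reproduce?** No. Section 7.1 gives no sample-size or power calculation, and the documents state no background symptom rate. What follows shows scale and is not an estimate.

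**3. Formula.** Let v be the proportion with a vaccine-caused symptom, and b the proportion whose symptom is present at the dose and persists into the diary period, assumed independent of v.

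- Reported proportion = 1 - (1 - v)(1 - b)
- Excess over v = b(1 - v)

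**4. Inputs.** For v, the rates that Section 1 quotes for ages 5-11 from an earlier trial: fever 2.5% (dose 1) and 6.5% (dose 2), headache 22.4% (lower end), fatigue 33.6% (lower end). For b, an assumed range of 1% to 10%.

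**5. Results, excess in percentage points.**

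| Symptom, v | b = 1% | b = 2% | b = 5% | b = 10% |
|---|---|---|---|---|
| Fever, 2.5% | 0.97 | 1.95 | 4.88 | 9.75 |
| Fever, 6.5% | 0.94 | 1.87 | 4.68 | 9.35 |
| Headache, 22.4% | 0.78 | 1.55 | 3.88 | 7.76 |
| Fatigue, 33.6% | 0.66 | 1.33 | 3.32 | 6.64 |

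Example: headache at b = 5% gives 0.05 × (1 - 0.224) = 0.0388, so 22.4% would be reported as 26.3%. One b need not suit all symptoms; the share of children febrile at a vaccination visit may well differ from the share with a headache.

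**6. Sensitivity to v.** The Section 1 rates come from vaccine recipients and may already contain background. If the 22.4% already includes b = 5%, then v = (0.224 - 0.05)/0.95 = 18.3%, and the excess is 22.4 - 18.3 = 4.1 points instead of 3.9. The illustration barely moves; the unknown is b.

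**7. Why no count per dose is given.** The Protocol Summary and Section 3.1 enrol each child either at dose 1 or at a booster, and 320 is the total. The split is not stated, so neither a number of affected children per dose nor a precision per dose can be derived. For dose-1 fever at 2.5%, the Clopper-Pearson 95% half-width would be 1.9 points if all 320 enrolled at dose 1 and 2.8 points if half did (160, an assumption). Whether a given bias exceeds sampling error depends on that split.

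**The case against.** **POM 1-3 are not miscounted.** They are occurrence measures, and no planned table uses relatedness for solicited events. This stands. A reader might infer that the primary outcomes are calculated wrongly; the documents do not support that. The bias appears when the counts are read as reactions, which is the reading that the causality paragraph adopts.

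**The subgroup comparisons are not shown to be biased.** A reader might infer that the co-administration and serostatus contrasts inherit the error. With equal b in both groups, a difference shrinks only by the factor (1 - b): an illustrative 40% versus 30% becomes 43.0% versus 33.5% at b = 5%, a difference of 9.5 points instead of 10. Unequal b is conceivable, for instance if recently infected children are both seropositive and still symptomatic, but nothing in the documents establishes it.

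**Partial safeguards exist.** Section 5.5 asks families to document symptoms after the injection. Users of the web-based diary are phoned about Grade 3 events. COVID-19 diagnoses and concomitant medications are recorded at follow-up contacts. These may reveal some illness under way at the dose, but none is a baseline and none feeds a rule for counting events.

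**The form may already ask.** The memory aid and the comprehensive statistical analysis plan are not among the documents, so a pre-dose item or a new-onset rule could exist there. This cannot be excluded.

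**A baseline does not remove chance onsets.** Symptoms that start by coincidence after the dose would still be counted. True; the remedy is partial.

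**Conclusion.** The gap is real but narrower than it may first appear. The protocol schedules no pre-dose record of the Table 5 symptoms for any dose, deems all solicited symptoms related, and has no unvaccinated group. As counts of symptoms on Days 1-7, POM 1-3 stand. As proportions with a vaccine reaction, they are too high to the extent that symptoms were already present at the dose.

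The direction is upward; the size is unknown. The figure of 3.9 points for headache rests on an assumed b of 5%, on persistence to the first diary entry, on independence from any reaction, and on an earlier trial's rate used as v. The point mainly concerns Table 5; injection-site findings are seldom present before the injection. It is worth acting on because the information cannot be recovered later and is cheap to collect, subject to confirming that the memory aid does not already collect it.

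**What to change.** 1. Check the memory-aid form and the separate statistical analysis plan for a pre-dose item or a new-onset rule. If both exist, cite them in Sections 5.5 and 7.2.2.
2. Otherwise, add to the Day 1 memory-aid page, for dose 1, dose 2 and booster, a yes/no and grade entry for each Table 5 symptom asking whether it was present before that day's vaccine. It belongs on the diary because Visit 1 can fall up to 3 days before the dose and Visit 2 up to 3 days after. For the same reason, a temperature taken by staff at Visit 1 would not serve: it could not cover dose 2, or a first or booster dose given after that visit.
3. In Section 7.2.2, report POM 1-3 twice: all reported events as now, and events that are new or of higher grade than the pre-dose entry.
4. In the causality paragraph of Section 5.5, limit the relatedness statement to new or worsened symptoms. If no pre-dose record is added, drop the blanket statement and describe the results as symptoms following vaccination.

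**Cost.** One diary column of 11 items per dose and one further table; no extra visit or staff. The downsides are slightly more burden on Day 1, reliance on the family's recall of the pre-dose state, and coincidental onsets after the dose that remain uncorrected.

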1 BACKGROUND

As of September 2022, there have been more than 95 million cases of COVID-19 leading to more than one million deaths in the United States (1). Although COVID-19 infection is generally milder in children than adults, it does cause significant pediatric morbidity and mortality. The American Academy of Pediatrics reports that 15 million children have been infected during the pandemic (2), leading to nearly 9000 cases of multisystem inflammatory syndrome in children (MIS-C) and 1500 deaths. From this perspective, safe and effective pediatric COVID-19 vaccines are needed to curb the pandemic.

In May 2021, the FDA issued an Emergency Use Authorization (EUA) for the Pfizer-BioNTech (Pfizer) mRNA COVID-19 vaccine in children aged 12-15. In the Phase III trial leading to the EUA, 2,260 adolescents 12-15 years old were randomized 1:1 to receive 2 doses of 30 ug of the BNT162b2 vaccine or placebo administered 3 weeks apart (3). Pain at the injection site was the most common local reaction, occurring in 86% of vaccine recipients after dose 1, and was somewhat less common after dose 2 (79%). Fatigue (60%), headache (55%), and chills (28%) were the most common systemic events after dose 1. These were slightly more common after dose 2 (fatigue (66%), headache (65%), and chills (42%).

On October 29, 2021 the FDA issued an EUA for the Pfizer-BioNTech vaccine in children aged 5-11 years old, administered as 2 doses of 10 ug 3 weeks apart. The main safety study randomized children 2:1 to BNT162b2 (N=1518) vaccine or placebo (N=750); children were followed for at least 2 months after dose 2. In general, children had less severe systemic reactions than adolescents and young adults following the age-appropriate dose. The most common systemic reactogenicity events in children aged 5-11 years after were fatigue (33.6-39.4%) and headache (22.4-28%). In children aged 5-11 years fever was infrequent after dose 1 (2.5%) and dose 2 (6.5%). There were no serious adverse events in the pediatric study that were considered related to the BNT162b2 study vaccine. No cases of myocarditis or anaphylaxis occurred in the study (4).

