- Obtain parental permission by written informed consent and a release of medical record information, based on site IRB requirements
- Obtain assent from child, based on site IRB requirements
- Review and confirm study eligibility
- Obtain information on preferred method of contact for follow-up (telephone or email, or text reminder reminder)
- Obtain demographic data & COVID-19 vaccine history
- Obtain history of vaccines within 2 weeks of enrollment
- Obtain medical history, including COVID-19 disease history
- Obtain concomitant medication and vaccine use
- For children at participating sites, obtain optional blood sample within 3 days before or after vaccination for serologic analysis
- Dispense thermometer, ruler (in order to standardize measurements) and memory aid. Review instructions for use of thermometer, ruler, and memory aid completion. Preference will be to complete the memory aid electronically, with paper as a back-

up.

- Confirm anticipated date of COVID vaccine, if not already occurred
- Confirm date of next scheduled study visit

Visit 1a, Days 1-7 after dose 1 (Phone Visit)

- Subjects/parent/LAR will complete their memory aid via paper or electronic entry at approximately the same time each day for days 1-7, study staff will review subject-entered data within the database or by phone contact
- For participants using REDCap web-based system:
 - Study staff will send daily reminders to fill out the symptom diary
 - Record clinical data related to COVID diagnoses
 - Study staff will review REDCap system to confirm data capture and assess for any AE, AESIs, or SAEs on day 3 and 7 after vaccine
 - If any missing values, reported hives, or Grade 3 events occurred, the study staff will use phone contact to gather more information
 - The first parental and adolescent (if applicable) survey will be administered on day 7 after vaccine
 - Study staff will verify date of next COVID-19 vaccine and remind subjects to complete memory aid with next dose
- For participants using paper diary:
 - Study staff will call participants on day 3 after vaccine as a reminder to fill out the symptom diary
 - The first parent and adolescent (if applicable) survey will be administered on day 7
 - Study staff will call participants on day 7 (+ 3 days)
 - Record symptom diary
 - Record COVID-19 diagnoses
 - Record first parental and adolescent (if applicable) survey
 - Verify date of next COVID-19 vaccine and remind subjects to complete memory aid with next dose

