- Dispense thermometer, ruler (in order to standardize measurements) and memory aid. Review instructions for use of thermometer, ruler, and memory aid completion. Preference will be to complete the memory aid electronically, with paper as a back-up.
- Confirm date of next scheduled study visit

Visit 1a, Days 1-7 after dose 1 (Phone Visit)

- Subjects/parent/LAR will complete their memory aid via paper or electronic entry at approximately the same time each day for days 1-7, study staff will review subject-entered data within the database or by phone contact
- For participants using REDCap web-based system:
 - Study staff will send daily reminders to fill out the symptom diary
 - Record clinical data related to COVID diagnoses
 - Study staff will review REDCap system to confirm data capture and assess for any AE, AESIs, or SAEs on day 3 and 7 after vaccine
 - If any missing values, reported hives, or Grade 3 events occurred, the study staff will use phone contact to gather more information
 - The parental and adolescent (if applicable) survey will be administered on day 7 after vaccine
 - Study staff will verify date of next study visit
- For participants using paper diary:
 - Study staff will call participants on day 3 after vaccine as a reminder to fill out the symptom diary
 - The parent and adolescent survey (if applicable) will be administered on day 7
 - Study staff will call participants on day 7 (+ 3 days)
 - Record symptom diary
 - Record COVID-19 diagnoses
 - Record parental and adolescent survey (if applicable)

Visit 2, 28 Days (window days 29-35) after COVID-19 Booster (Clinic Visit or Phone Visit)

- Clinic visit for optional post-vaccination blood draw for immunogenicity studies
- If no blood draw, may be a phone visit
- Review concomitant medications and vaccinations.

- Solicit for the occurrence of any adverse events of special interest or serious adverse events.

Visit 3, 180 days (window Days 174 - 188) after COVID-19 Booster (Phone Visit)

- Record any SAEs or adverse events of special interest as described in **Section 5.5**
- Obtain concomitant medication and vaccine use

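### Section 5.5 requires one routine temperature a day and no reading when the child feels feverish or has chills, so short fevers may be missed and detection is left to each family.

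*Combined protocol and SAP*

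**What the plan says.** Section 5.5 has families record oral temperature with the study thermometer for seven days after each dose. Recording starts "Beginning on the evening following the first COVID-19 vaccination", which is the only hint of a clock time. The routine reading is daily: "Temperature will be recorded at roughly the same time each day". The visit descriptions in section 5.1 put the diary on the same rhythm, completed "at approximately the same time each day for days 1-7".

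Two sentences deal with further readings. After a value above 100°F (37.8°C), "a second measurement will be taken"; neither its timing nor its purpose is given. The next sentence covers any additional reading, for whatever reason it was taken: "If more than one temperature is taken on the same day, the highest temperature should be recorded".

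Fever requires a measurement ("Fever will be defined as a measured temperature" of 100.4°F or more). Table 5 grades fever by temperature. It solicits feverishness and chills as separate rows, graded by interference with activity. Section 7.2.2 summarises each event by its maximum grade over days 1-7.

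**The concern.** Fever is the only row of Table 5 graded by an instrument. If no reading is taken while the child is febrile, the fever row shows none, whatever the parent noticed. Yet the two symptoms most likely to alert a parent, feverishness and chills, are already solicited and are not tied to a reading. A fever overnight or during school hours that has settled by the routine reading is recorded only if someone chose to measure.

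Two things are at stake. The fever proportion in POM 1, and through it POM 2 and POM 3, may be too low. And the number of readings per child rests on family habit, so the chance of detecting the same fever may differ between participants. If that habit differed between families whose child had other vaccines on the same day and those whose child did not, it would enter the comparison in section 7.2.3.

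**Working it through.** The plan gives no fever error rate, fever duration or sample-size calculation (section 7.1), so it has no figure to reproduce. The check sets out what the text requires and then illustrates the size under stated assumptions.

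**1. What is required and what is optional**

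| Situation | Reading required? | If a reading is taken |
|---|---|---|
| Daily routine time | Yes | Recorded |
| After a reading above 100°F | Yes, one repeat | Day's highest kept |
| Child feels feverish or has chills at another time | Not stated | Day's highest kept |

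The third row is the gap. Such readings are neither forbidden nor discarded; they are not asked for.

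**2. Short fevers: worst case**

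Assumptions, none from the documents: one reading per 24 hours, one episode of D hours, onset uniform over the day, no extra readings. Then P(captured) = min(1, D/24).

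For scale, section 1 cites fever after dose 2 in 6.5% of children aged 5-11 in the earlier vaccine trial. Treating that as a true rate in all 320 planned participants gives 0.065 × 320 = 20.8 children. This is a scale only: the cohort also includes older children and booster recipients, and 6.5% is itself a recorded rate.

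| D (hours) | Captured | Of 20.8 children | A true 6.5% would show as |
|---|---|---|---|
| 4 | 4/24 = 17% | 3.5 | 1.1% |
| 6 | 6/24 = 25% | 5.2 | 1.6% |
| 8 | 8/24 = 33% | 6.9 | 2.2% |
| 12 | 12/24 = 50% | 10.4 | 3.3% |
| 24 or more | 100% | 20.8 | 6.5% |

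Every extra reading taken during a fever moves the result toward full capture. An evening reading may also not be random relative to onset.

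**3. The repeat above 100°F**

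The maximum of two readings is never below the first, so the repeat can leave, add or upgrade fever but cannot remove it. In 1,000,000 simulated pairs no value or grade was lowered. To see whether averaging the two readings would be better, assume normal reading error with SD s = 0.2, 0.3 or 0.4°F around a true temperature T, and let p1 = P(one reading ≥ 100.4).

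- As written: P(fever) = p1 + [P(first > 100.0) − p1] × p1.
- Averaging: P(first > 100.0 and mean of two ≥ 100.4).

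Example, T = 100.6°F and s = 0.4: p1 = 0.6915 and P(first > 100.0) = 0.9332, so P(fever) = 0.6915 + 0.2417 × 0.6915 = 0.8586.

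| T | Single reading | As written | Averaged |
|---|---|---|---|
| 100.2°F (not fever) | 16 / 25 / 31% | 27 / 38 / 43% | 8 / 17 / 23% |
| 100.6°F (fever) | 84 / 75 / 69% | 97 / 92 / 86% | 92 / 82 / 75% |

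(Entries are for s = 0.2 / 0.3 / 0.4°F.) The rule as written labels more borderline non-fevers as fever and detects more true low-grade fevers. Averaging reverses both.

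**The case against.** The strongest reply is that the text already accommodates the fevers in question. A parent who measures a hot child at night records that value, because the day's highest is kept. Families are trained on the thermometer and memory aid, and the memory aid is not among the documents, so it may already contain such a prompt. Feverishness and chills are solicited without a reading, so the illness episode is not lost. POM 2 and POM 3 are composites over 16 solicited items (five in Table 4, eleven in Table 5), so a missed measured fever changes them only when no other item reaches the same grade. One rule applies to both co-administration groups, and section 7.2.3 calls that assessment descriptive.

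Most of this stands as a limit on size. It does not close the gap: feverishness is not measured fever, and a rule that is the same on paper but leaves extra readings to choice does not give the same detection in every child.

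Two stronger readings are tempting. One is that fevers between readings are lost by design, with capture of 33-50%. The documents do not support this, because extra readings are allowed and kept; those rates are a worst case. The other is that the repeat rule biases fever upward and should be replaced by averaging. It is true that a repeat can only leave, add or upgrade fever. But the interval before the repeat is not stated, keeping the highest fits an endpoint based on maximum grade, and averaging gives up sensitivity for true low-grade fever. That is a trade-off, not an error in the plan.

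**Conclusion.** The point holds in a limited form. The required schedule is one routine reading a day, with no prompt at the moment when a fever is most likely to be present. Short fevers may therefore go unmeasured, and the chance of detection may vary between families.

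The size cannot be fixed from the documents. The upper bound on the loss is 50-67% of fevers lasting 8-12 hours, and it rests on uniform onset and no extra readings at all. Missed short fevers and the highest-value repeat push the fever proportion in opposite directions, so the net direction of bias is unknown. No differential effect on the co-administration comparison is shown, only an open route to one. The direct effect is on the fever row of Table 5 and POM 1, with a smaller possible effect on POM 2 and POM 3. The point is worth acting on because the remedy is cheap, not because the fever endpoint is unusable.

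**What to change.** Add one instruction to section 5.5 and to the memory aid: besides the daily reading, take the child's temperature whenever the child feels feverish or has chills, and record the highest value of the day as now. If the memory aid already says this, bring section 5.5 into line with it. Leave the repeat and the highest-value rule unchanged.

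The cost is a wording change and a few extra readings for families. The number of readings will then depend on symptoms, so a more symptomatic group will be measured more often. That dependence already exists informally; the change makes the trigger the same for every family, and the report should state it when fever is compared by co-administration status.
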